### 5.3. Screening Period

#### 5.3.1. Telephone Screen

Individuals who call the lab (in response to flyers and advertisements) expressing interest in the study will receive detailed information about the study procedures, and if they remain interested they will complete a telephone screen performed by a trained research assistant for self-reported inclusion and exclusion criteria. Those who appear eligible will be invited to the laboratory for an initial in-person screening session.

#### 5.3.2. Initial Screening Visit

Prior to conducting any research related procedures, research staff will conduct the informed consent process, which details the procedures to take place during the screening visit. The initial screening visit may take place in-person or virtually over Zoom. At an in-person visit, informed consent will be a three-part process. First, participants will be asked to read and provide verbal consent for breathalyzer. If the breathalyzer is above 0.000, the visit will be stopped and the participant will not be compensated. The participant will be given an opportunity to reschedule the visit for another day. If the breathalyzer test is negative, the written informed consent form will be reviewed and signed by the participant and study staff

outlining procedures for the initial screening visit. At the initial screening visit, subjects will be asked to provide a urine sample to test for drugs of abuse and pregnancy (if female), and will complete a series of individual differences measures (described in detail below). This visit should take approximately 2 hours.

Initial screening visits may also take place remotely. In this case, participants will be provided with a Zoom link to meet with a researcher. Participants will be asked to confirm that they have not consumed alcohol or any illicit substances prior to the study visit. They will not provide breathalyzer or urine samples in a virtual visit, but these elements will be included in the medical screening visit if participants are otherwise eligible. In the event of a virtual screening visit, participants will be emailed a PDF copy of the initial visit consent form. After reviewing the consent form with study staff, participants will type their names onto a signature page to indicate their agreement and consent to participate in the screening visit. Typing their name on the signature page will serve as an electronic signature.

Following the initial screening visit, the study coordinator will meet with the PI to determine if the participant is eligible to continue to the medical screening based on study inclusion/exclusion criteria. A second written consent form will be reviewed and signed in the presence of the study physician or nurse practitioner at the medical screening visit if the participant is found eligible to continue to that visit.

### 5.3.3. Medical Screening Visit

Those participants who appear to be eligible after the initial screening visit, will then be scheduled for a second screening visit. This visit will be conducted in the research lab and CTRC by the study physician (MD) or nurse practitioner (NP) and will start with a breathalyzer test. If the breathalyzer is above 0.000, the visit will be stopped and the participant will not be compensated. The participant will be given an opportunity to reschedule the visit for another day. If the breathalyzer test is negative, the MD or NP will conduct the second written (experimental) consent; medical history interview and physical exam. In addition, a urine drug screen test will be repeated. At the CTRC, a blood specimen will be collected for a Comprehensive Metabolic Panel and Complete Blood Count to evaluate overall health; and will obtain an EKG to screen for medical conditions that could make study participation medically unsafe. The MD or NP will review each participant's medical history, vital signs, weight, review of systems, and laboratory tests, including liver function tests (LFTs), drug screen, chemistry screen, and urine pregnancy screen to determine if it is medically safe for the participant to take the study medication.

Any subject who is excluded from the study will be compensated for their time in the screening session and will be offered referrals for alcohol treatment in the community.

## 5.4. Experimental Visit

### 5.4.1. Randomization

Participants who are eligible after the physical exam will be randomized to an experimental condition (i.e., endotoxin vs. placebo) within an appropriate amount of time based on study physician discretion. Urn randomization will be used to balance the two groups by gender and BDI-II severity. The UCLA Research Pharmacy will manage the blind. The two treatment conditions will not be different in appearance or method of administration. However, it is

possible that participants undergoing the endotoxin challenge who feel very symptomatic may suspect that they are in the active condition. For this reason, we have decided to exclude individuals who experience severe sickness symptoms as described below (which is expected to be less than 5% of the sample). If participants are withdrawn from the study due to sickness symptoms, their data will be retained for the purposes of reporting adverse events and safety data during the trial. Additional subjects will be recruited to replace the withdrawn individuals.

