### 4. STUDY DESIGN

#### 4.1. Design Overview

The study design consists of a randomized, double-blind, placebo-controlled trial of low dose endotoxin. The low dose endotoxin challenge induces a transient systemic inflammatory response with normalization of cytokine levels within hours. This “phasic” inflammation is distinct from chronic (“tonic”) levels of inflammation that may be present with AUD. A total of 38 non-treatment seeking heavy drinking men and women and 38 light drinking healthy controls will participate in the study. Recruitment will be monitored to ensure the two groups are matched by gender. Eligible participants will be randomly assigned to receive a single I.V. infusion of either low dose endotoxin (0.8 ng/kg of body weight) or placebo (same volume of 0.9% saline solution) at the UCLA Outpatient Clinical and Translational Research Center (CTRC). All participants will complete an alcohol cue-exposure paradigm 2 hours post infusion, which is the time of expected peak cytokine response (13, 14). Participants will complete the fMRI alcohol cue reactivity paradigm 3 hours post infusion. Plasma levels of proinflammatory cytokines [i.e.,

Interleukin-6 (IL-6) and tumor necrosis factor- $\alpha$  (TNF-  $\alpha$ ), mood, reward reactivity, and alcohol craving, will be assessed at baseline and then hourly for four hours post infusion.

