### **8.1. Statistical Power**

A power analysis was conducted for the study based on results from a previous human endotoxin challenge carried out in a control sample by our collaborators ([name] et al., 2010). Effect size was calculated based on [name] et al.'s reported sample size of  $N = 39$  and  $F$ -statistic of 8.13 for increase in negative mood at T2 after endotoxin infusion, yielding Cohen's  $d = 0.4687$ . Power analysis was conducted according to Cohen's guidelines to determine the sample size needed to achieve a power  $\geq 0.80$  (i.e. 80%) at an alpha level of .05. Using the program G\*Power version 3.1 and selecting the repeated measures ANOVA, within-between interactions design, where alpha = .05, effect size  $f = 0.234$ , we arrived at a total  $N = 76$  completers (38 heavy drinkers and 38 healthy controls). Specifically, we powered the study

to detect differences from baseline to peak (T2) inflammatory response, given that the remaining data points post-peak tend to be similar and may obscure the effects of the inflammatory challenge. Individuals who experience severe sickness symptoms will be excluded (expected to be <5% of the sample).

**8.2. Aim 1: To test that low dose endotoxin will increase cue-induced craving for alcohol in heavy drinkers as compared to light drinking controls, and as compared to placebo.**

Repeated measures analyses of variance (ANOVAs) will be conducted using PROC GLM in SAS Statistical Software. Specifically, in the repeated measures ANOVA models, Group (Heavy drinking versus light drinking) will be a two level between-subjects factor, Treatment (endotoxin vs. placebo) will be a two level between-subjects factor, and Cue (water cues versus alcohol cues) will be a between-subjects factor. The dependent measure will be self-reported alcohol craving captured by the Alcohol Craving Questionnaire. Sickness symptoms and drinking history (i.e., drinks per day and drinks per drinking day in past year) will be used as covariates in these analyses.

**8.3. Aim 2: To test whether low dose endotoxin (0.8 ng/kg of body weight) will increase depressed mood as compared to placebo.**

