Repeated measures ANOVAs in which Group (Heavy drinking versus light drinking) will be a two level between-subjects factor, and Treatment (endotoxin vs. placebo) is a two level between-subjects factor. The outcome measure is depressed mood (captured by the POMS). Sickness symptoms and drinking history will also be included as covariates in these analyses.

**8.4. Exploratory Analysis: To test associations between plasma levels of proinflammatory cytokines (IL-6 and TNF- $\alpha$ ), depressed mood, and alcohol craving during the challenge; and examine sex differences in responses to the endotoxin challenge.**

Repeated measures ANOVAs will be used to capture the effects of Treatment (endotoxin vs. placebo) by Time (T0 to T2) for the proposed planned outcomes (i.e. proinflammatory cytokines, hourly craving scores) as well as models that include sex as a between-subjects factor. As with the primary aims, sickness symptoms and drinking history will be entered in these models as covariates.

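### The urn balances treatment on gender and BDI-II but not within drinker group, and neither primary model includes the two factors it does balance on

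*Combined protocol and SAP*

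**What the plan says.** **Allocation.** Section 5.4.1 says that eligible participants "will be randomized to an experimental condition (i.e., endotoxin vs. placebo") and then: "Urn randomization will be used to balance the two groups by gender and BDI-II severity". Since treatment is what is being randomised, the two groups in that sentence are the endotoxin and placebo arms. No section names drinker group as an urn variable or describes separate randomisation of heavy and light drinkers.

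**Sample.** Section 4.1: "A total of 38 non-treatment seeking heavy drinking men and women and 38 light drinking healthy controls will participate in the study". It adds "Recruitment will be monitored to ensure the two groups are matched by gender", which concerns the heavy and light groups at recruitment. Arm totals, allocation ratio, urn parameters and the BDI-II cut-point are not stated.

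**Primary models.** In both 8.2 (Aim 1) and 8.3 (Aim 2), "Group (Heavy drinking versus light drinking) will be a two level between-subjects factor", with Treatment as a second between-subjects factor. The covariates named are sickness symptoms and drinking history. Neither gender nor BDI-II is listed.

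**Other models.** The fMRI analysis (8.5) and the reward analysis (8.6) also use Group and Treatment, without gender or BDI-II. The exploratory analysis in 8.4 is Treatment by Time, names no Group factor, and adds models with sex as a factor.

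**The concern.** Allocation and analysis use different factors. Aim 1 asks about endotoxin against placebo and about heavy against light drinkers, so its precision depends on how evenly treatment is spread within each drinker group. Nothing in the allocation secures that, although the AUDIT is completed at the initial screening visit (6.2.5) and randomisation comes only after the physical exam (5.4.1). Uneven cells widen the standard error of the Group by Treatment contrast and make the two factors mildly non-orthogonal.

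In the other direction, an analysis that ignores the factors used to restrict randomisation tends to report standard errors that are too large when those factors are prognostic. BDI-II is a plausible predictor of depressed mood, the Aim 2 outcome.

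What is at stake is precision, in a study sized for power of at least 0.80.

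**Working it through.** **1. The plan's own figure.** Inputs from 8.1: f = 0.234, power at least 0.80, "at an alpha level of .05", "selecting the repeated measures ANOVA, within-between interactions design", and an aim "to detect differences from baseline to peak (T2) inflammatory response", hence m = 2 measurements. The number of groups k and the correlation ρ between measurements are not given. The noncentrality is λ = f²·N·m/(1−ρ), with df1 = (k−1)(m−1) and df2 = (N−k)(m−1).

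- k = 2, ρ = 0: smallest N is 74. At N = 76, λ = 0.054756 × 76 × 2 = 8.32 and power is 0.813.
- k = 2, ρ = 0.5: N = 38, which doubled for two drinker groups is 76.
- k = 4 (the Group by Treatment cells), m = 2: N = 104, 80 and 56 at ρ = 0, 0.25 and 0.5. None gives 76.
- k = 4, m = 4, ρ = 0 also gives 76, but four measurements do not fit a baseline-to-T2 comparison.

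So 76 is reproducible, but only under assumed settings.

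**2. How uneven the cells can become.** Let x be the number of the 38 heavy drinkers given endotoxin; an even split is 38/2 = 19 (inferred, not stated in the plan).

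| Allocation assumed | SD of x | 95% range | Chance of 15/23 or worse |
|---|---|---|---|
| Arms forced to 38/38 (hypergeometric) | 2.19 | 15–23 | 10.8% |
| Simulated urn on gender and BDI-II | 2.50 | 14–24 | 15.7% |
| No forced balance (binomial, 1:1) | 3.08 | 13–25 | 25.6% |

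For the first row, the variance is 38 × 0.5 × 0.5 × 38/75 = 4.81. The urn simulation used 4,000 runs and assumed 50% women, 30% with higher BDI-II, one starting ball and one ball added per assignment.

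**3. What an uneven split costs.** Relative efficiency of a split a/(38−a) in both drinker groups is 4a(38−a)/38². Writing a = 19 ± d, this equals 1 − d²/361.

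- Average loss with arms at 38/38: 4.81/361 = 1.3%, about one participant in 76. For the simulated urn it is 1.7%.
- 15/23: 1380/1444 = 0.956, a loss of 4.4%, or variance higher by 1/0.956 − 1 = 4.6%.
- 13/25: 1300/1444 = 0.900, a loss of 10%.

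Power, by noncentral F with λ multiplied by the relative efficiency:

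| Split | Within one drinker group of 38, ρ = 0.5 | 1-df contrast on 76, ρ = 0 |
|---|---|---|
| 19/19 | 80.2% | 81.2% |
| 17/21 | 79.7% | 80.8% |
| 15/23 | 78.4% | 79.5% |
| 13/25 | 75.9% | 77.1% |

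**4. What the allocation fix buys.** In the same simulation, adding drinker group to the urn narrows the range from 14–24 to 15–23 and cuts the chance of 15/23 or worse from about 16% to about 5%. Mean power of a nominal 80% Group by Treatment contrast rises only from 79.3% to 79.6%.

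**5. What adjusting for the urn factors could buy.** If they explain a share R² of the variance of the quantity tested, a test with 80% power rises to Φ((1.960 + 0.842)/√(1−R²) − 1.960). That is 82%, 84% and 88% at R² = 5%, 10% and 20%. These R² values are assumptions; the documents give none.

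**The case against.** The strongest objection is size. Balancing on drinker group is worth about 0.3 points of power on average, assignment is random, Group is already in both primary models, and the general linear model carries mild non-orthogonality into the standard errors. Section 8 also plans baseline equivalence checks, and 4.1 matches the drinker groups by gender. The argument on size stands. The other two provisions do not close the gap: baseline checks reveal imbalance without preventing or adjusting for it, and gender matching at recruitment says nothing about treatment within each drinker group.

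Three stronger readings are tempting, and the documents do not support them.

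- A reader might infer that every analysis crosses drinker group with treatment and that no model contains an urn factor. Section 8.4 contradicts both: it names no Group factor and includes models with sex.
- A reader might infer that the treatment estimate is biased or the test invalid. Random assignment rules out the first. Omitting balancing factors errs towards conservatism.
- A reader might expect a large gain from adjusting for BDI-II in Aim 2. An assumed correlation of 0.4 to 0.6 with POMS depression would account for 16% to 36% of variance at a single time point (0.4² to 0.6²). No such correlation is in the documents. Section 8.1 powers change from baseline to T2, where stable between-person differences largely cancel, and 5.2.2 excludes BDI-II scores of 21 or more, which narrows the range.

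**Conclusion.** The point holds as a modest, low-cost improvement. Treatment is not balanced within drinker group, a factor in both primary models, and the two factors that steer allocation are in neither of those models. The treatment effect is not biased.

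With arms held at 38/38, the expected efficiency loss is about 1%, rising to 4–5% at the edge of the 95% range (15/23), where power falls by just under two points. If nothing forces balance, a 13/25 split would cost about four points. These figures rest on 1:1 allocation and the arm totals, neither of which is stated, and for the urn row on assumed urn settings.

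The loss from omitting gender and BDI-II depends on how well they predict the tested outcome, which cannot be sized from the documents. Whether sickness symptoms belong among the covariates is a separate question and is not decided here.

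**What to change.** In 5.4.1, add drinker group (heavy or light) as a third urn variable, or run a separate urn in each drinker group. If enrolment has begun, apply this to participants still to be randomised. State the allocation ratio and the BDI-II cut-point there as well.

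In 8.2 and 8.3, add gender and baseline BDI-II score as pre-specified covariates, keeping Group as a factor. Specifying them now avoids a choice made after seeing the data.

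The cost is one setting in the pharmacy's randomisation, a few sentences of SAP wording, and two model degrees of freedom. Both measures are already collected at the initial screening visit, so no participants, visits or assessments are added, and the sample size is unchanged.

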#### **6.2.31. Physical Sickness Symptoms Assessment**

Symptoms of physical sickness will be self-reported during each experimental visit on a scale from 0 (symptom not present) to 4 (very severe) at multiple time points (baseline, T1, T2, T3 and T4). At the baseline assessment, participants must have a total score below 10 in order to move forward with the experimental challenge. Scores of 10 or above will result in the visit being rescheduled when the participant is feeling better. Participants who rate any symptom as a '4' at the T1 – T4 assessment will be withdrawn from the study prior to the cue-reactivity paradigm. Research staff will contact the study physician and/or nurse practitioner on call to manage any severe sickness symptoms reported during the experimental session.

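### Randomised, infused participants who react severely are excluded and replaced, so the primary analyses no longer compare the groups as randomised, and some T2 data already collected would be discarded

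*Combined protocol and SAP*

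**What the plan says.** Section 5.4.1 gives protection of the blind as the reason for the exclusion. It is "possible that participants undergoing the endotoxin challenge who feel very symptomatic may suspect that they are in the active condition", and so "we have decided to exclude individuals who experience severe sickness symptoms as described below". On the data of those withdrawn it says "their data will be retained for the purposes of reporting adverse events and safety data during the trial", and names no efficacy use. It then adds: "Additional subjects will be recruited to replace the withdrawn individuals".

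Section 6.2.31 gives the working rule. "Participants who rate any symptom as a '4' at the T1" to T4 assessments "will be withdrawn from the study prior to the cue-reactivity paradigm". The rule applies to every participant, whatever the arm.

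Section 8.1 repeats the exclusion, "Individuals who experience severe sickness symptoms will be excluded (expected to be <5% of the sample"), and sizes the trial as 76 completers. Section 8 defines no analysis set of all randomised participants, no rule for missing data, and no sensitivity analysis that brings the excluded participants back.

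The post-infusion cue session is at 2 hours (Sections 4.1 and 5.4.5; T2 only in the Section 6.1 schedule). POMS is collected at baseline and at T1 to T4 (Section 6.2.35). Section 5.4.3 has a separate individual stopping rule based on serious and Grade 3 events, which is not linked to the rating-of-4 rule.

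**The concern.** Whether a participant stays in the analysis depends on something that happens after infusion and that the infusion itself can cause. The stated reason is about people given endotoxin, so removals will be concentrated in that arm. Replacement restores the head count but not the comparison. Someone who stays in on endotoxin has been selected for tolerating it, and the placebo arm gets little matching selection. Both primary aims, craving and depressed mood, use the same depleted set.

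The timing raises a second problem. Withdrawal before the cue session is impossible for someone whose first 4 comes after it. As written, the plan would exclude people who already have complete baseline and T2 data, which is the contrast that Section 8.1 says the study is powered on.

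The exclusion also does little for the blind. It removes an expected few percent, while participants with lesser symptoms, who may also guess their arm, remain.

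**Working it through.** **1. The plan's own figures.** Section 8.1 gives f = 0.234, d = 0.4687, alpha .05, power of at least 0.80 and 76 completers. It does not state the number of groups, the number of measurements or the correlation between them.

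- Within-between interaction formula: noncentrality = f² × N × m / (1 − rho).
- Two groups, m = 2, rho = 0: N = 74, with power 0.813 at 76.
- Four groups, m = 2, rho = 0.3: N = 76 in equal cells, power 0.814.
- m = 2, rho = 0.5: N = 38 (two groups) or 56 (four equal groups).

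So 76 can be reached, but only with inputs the plan does not give. For that reason I do not convert the shift below into a loss of power.

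**2. How many people.** 3/76 = 3.9% and 4/76 = 5.3%, so fewer than 5% of 76 means at most 3. Counting withdrawals on top of 76 completers gives the same answer: 3/79 = 3.8%, and 4/80 = 5.0%, which is not below 5%. The allocation ratio is not stated. Assuming 1:1, 38 receive endotoxin, and if all exclusions fall there, q = 3/38 = 7.9%. If the 38 are completers and the 3 are extra, q = 3/41 = 7.3%.

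**3. Size of the shift.** Assume that sickness is roughly normal within the endotoxin arm, that its top share q is removed, and that it correlates r with outcome. The documents give no r. The unadjusted endotoxin mean then moves by −r × φ(z)/(1 − q), where z is the (1 − q) normal quantile. For q = 0.0789, z = 1.412, φ(z) = 0.1472, and φ(z)/(1 − q) = 0.1598.

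| r | shift (SD) | share of 0.4687 |
|---|---|---|
| 0.3 | 0.048 | 10% |
| 0.5 | 0.080 | 17% |
| 0.7 | 0.112 | 24% |

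The standard error of a 38 versus 38 difference in means is √(2/38) = 0.23 SD, so the shift is half of that or less. The last column takes the plan's d at face value. However, √(8.13/37) = 0.4687. If the source F is a two-group test with 37 error degrees of freedom, that quantity is closer to f, and d would be twice as large (0.94). The shares would then halve, to about 5% to 12%.

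**4. Direction.** These shifts shrink an endotoxin increase only if r is positive. If the sickest participants crave less, r is negative and exclusion inflates the estimate.

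**5. Timing of the first rating of 4.**

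| First 4 at | Cue and mood data at T2 | Effect of the rule as written |
|---|---|---|
| T1 | not yet collected | participant lost; T0 and T1 values unused |
| T2 | depends on order within the hour, which is not stated | unclear |
| T3 or T4 | complete | collected primary data discarded |

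The plan does not say how the expected fewer than 5% divide across these hours.

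**The case against.** The strongest objection is that the number involved is small and the shift above is unadjusted, whereas Sections 8.2 and 8.3 enter sickness symptoms as a covariate in both primary models. With a linear relation between sickness and outcome, selecting on a covariate already in the model leaves the adjusted treatment coefficient essentially unchanged. A simulation with an assumed 1.5 SD treatment effect on sickness and the top 10% of the endotoxin arm removed gives a change below 0.001.

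That stands as a limit on the arithmetic. It does not rescue the exclusion. The trigger is any single symptom rated 4, so a total-score covariate captures it only approximately. Sickness is also measured after randomisation, so the adjusted coefficient is not the total effect of endotoxin, and any unadjusted or baseline-adjusted comparison remains exposed.

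Three stronger readings are tempting, and the documents do not support them:

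- **That only endotoxin participants are removed.** The rule makes no reference to arm, and a placebo participant can rate a symptom 4. Predominantly endotoxin is as far as the text goes.
- **That the strongest responders are removed, biasing towards the null.** This is true of sickness only. Nothing links severe sickness to greater craving or mood response, and Section 2.7 reports that endotoxin reduced the neural response to monetary reward but raised it to positive social feedback.
- **That valid T2 data are discarded for everyone excluded.** After a 4 at T1 there are no T2 data to discard.

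A mixed model is also no remedy for Aim 1. Cue data exist only at T0 and T2, so someone withdrawn at T1 contributes a baseline cue session and little else.

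**Conclusion.** The point holds. The plan excludes and replaces randomised, infused participants because of a post-infusion reaction, and provides no analysis that would show what this does to the result. Section 6.2.31 also contradicts the schedule: a first 4 at T3 or T4 cannot lead to withdrawal before a T2 session, and applying the exclusion there discards complete primary data.

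The likely size is modest and the direction unknown. On the plan's own expectation at most 3 people are affected, up to 7.9% of an assumed 38 on endotoxin, with an unadjusted shift of about 0.05 to 0.11 SD. That range assumes 1:1 allocation, all exclusions on endotoxin, and a correlation of 0.3 to 0.7 between sickness and outcome. The figure of fewer than 5% is an expectation, not a cap, so the effect grows if more participants react severely.

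**What to change.** - **Analysis set (5.4.1, 8.1, 8.2, 8.3).** Define the primary set as all randomised and infused participants, using every AUQ and POMS value observed. This includes the T2 data of anyone whose first 4 is at T3 or T4.
- **Replacements.** Count them as additional participants, not as substitutes for those withdrawn.
- **Reporting.** Give withdrawals by arm and time point.
- **Sensitivity analysis.** Show the protocol's exclusion here, alongside the primary result.
- **Model.** A likelihood-based mixed model may be used so that partial POMS and hourly AUQ data contribute. It adds little for the Aim 1 cue outcome.
- **Consistency.** Reconcile Sections 5.4.1, 5.4.3 and 6.2.31 on the trigger for withdrawal and its timing relative to the T2 cue session. No clinical withdrawal rule is proposed here; participants can still stop procedures as the investigators decide.

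The cost is analysis wording and one extra table. The downside is that a few observations will come from very symptomatic participants, and the sensitivity analysis shows how much they matter. A treatment-guess question would measure the blind directly, but it is optional and does not repair the exclusion.
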